7.2 Definitions

7.2.1Adverse Event (AE)

Any untoward or unfavorable medical occurrence associated with the subject's participation in the research, whether or not considered related to the subject's participation in the research (modified from the definition of adverse events in the 1996 International Conference on Harmonization E-6 Guidelines for Good Clinical Practice) (from OHRP "Guidance on Reviewing and Reporting Unanticipated Problems Involving Risks to Subjects or Others and Adverse Events (1/15/07)" http://www.hhs.gov/ohrp/policy/advevntguid.html#Q2)

7.2.1.1 Suspected Adverse Reaction (SAR)

Any adverse event for which there is a reasonable possibility that the investigational drug [or investigational study therapy regimen] caused the adverse event. For the purposes of safety reporting, 'reasonable possibility' means there is evidence to suggest a causal relationship between the drug and the adverse event. A suspected adverse reaction implies a lesser degree of certainty about causality than adverse reaction, which means any adverse event caused by a drug (21 CFR 312.32(a)).

7.2.2 Unexpected Adverse Event

An adverse event or suspected adverse reaction is considered "unexpected" if it is not listed in the Investigator Brochure or is not listed at the specificity, severity or rate of occurrence that has been observed; or is not consistent with the risk information described in the general investigational plan or elsewhere in the IND. "Unexpected" also refers to adverse events or suspected adverse reactions that are mentioned in the Investigator Brochure or package insert as occurring with a class of drugs or as anticipated from the pharmacological properties of the drug, but are not specifically mentioned as occurring with the particular drug under investigation (21 CFR 312.32(a)).

7.2.3 Serious Adverse Event (SAE)

An adverse event or suspected adverse reaction is considered "serious" if, in the view of either the investigator or Sponsor [DAIT/NIAID], it results in any of the following outcomes (21 CFR 312.32(a)):

- Death.
- A life-threatening event: An AE or SAR is considered "life-threatening" if, in the view of either the investigator or DAIT/NIAID, its occurrence places the subject at immediate risk of death. It does not include an AE or SAR that, had it occurred in a more severe form, might have caused death.
- Inpatient hospitalization or prolongation of existing hospitalization.
- Persistent or significant incapacity or substantial disruption of the ability to conduct normal life functions.
- Congenital anomaly or birth defect.
- Important medical events that may not result in death, be life threatening, or require hospitalization may be considered serious when, based upon appropriate medical judgment, they may jeopardize the subject and may require medical or surgical intervention to prevent one of the outcomes listed above.

Elective hospitalizations or hospital admissions for the purpose of conduct of protocol mandated procedures are not to be reported as an SAE unless hospitalization is prolonged due to complications.

7.2.4 Adverse Events of Special Interest (AESI)

Adverse Events of Special Interest will be collected and reported to the IND sponsor (NIAID), the NIAID Autoimmune DSMB, and to the manufacturer (Corbus Pharmaceuticals Holdings, Inc.).

- QTc prolongation > 500 msec total duration and > 60 msec from Visit 1 (Day 1) QTc interval prior to study drug administration
- Severe disease flares by SELENA SLEDAI Flare Index and/or a new BILAG A score except in musculoskeletal domain

• Aspartate aminotransferase or alanine aminotransferase $\ge 3 \times 10^{-10}$ x upper limit of normal and total bilirubin $> 1.5 \times 10^{-10}$ k the upper limit of normal, present on repeat testing

If an event meets any of the above AESI categories, regardless of the relationship of the event to the study drug or severity, the event must be reported to the IND sponsor (DAIT/NIAID) as described in Section 7.5.2, *Reporting of AESIs to DAIT/NIAID* and to Corbus Pharmaceuticals Holdings, Inc. as described in Section 7.5.5, *Reporting of Safety Information (AEs, SAEs and AESIs) to Corbus*.

7.3 Collection and Recording of Adverse Events

7.3.1 **Collection Period**

AEs of Grade 2 and above will be collected from time of signing of informed consent until the subject completes study participation, or until 30 days after he/she prematurely withdraws (without withdrawing consent), or is withdrawn from the study. See Section 7.4, *Grading and Attribution of Adverse Events* for grading criteria.

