- In JBT101-SSc-001, multiple different glucuronide metabolites of JBT-101 were observed in the plasma at < 10% with one glucuronide metabolite present at >10% at all doses. An open-label extension to the JBT101-SSc-001 study is ongoing, with 36 subjects enrolled as of July 2017. All subjects in the open-label extension receive JBT-101 20 mg once or twice per day, for up to 12 months. As of July 2017, total duration of double blind placebo controlled and open-label extension dosing with JBT-101 was median 234 days (range 28, 295 days). All 36 subjects had at least one open-label extension visit ≥ 28 days post baseline. Adverse events (AEs, n = 88) occurred in 28/36 (78%) subjects in the open-label extension. Most AEs were mild (55/88, 62%) or moderate (30/88, 34%) in severity and unrelated to JBT-101 (75/88, 85%). The AEs that occurred in ≥ 10% of subjects (n, % of subjects) were mild fatigue (5, 14%) and mild/moderate upper respiratory tract infection (4, 11%).

Study JBT101-CF-001 is a double-blind, placebo-controlled, randomised Phase 2 study conducted at 21 centres in the US and Europe. JBT-101 was administered at 1 mg once per day or 5 mg once per day for 28 days, escalating to 20 mg once per day or 20 mg twice per

day for an additional 56 days in subjects with cystic fibrosis. Eight-five subjects were dosed with study medication, the last subject has completed the trial, and it is estimated that ~61 subjects received JBT-101 and ~24 subjects received placebo throughout the trial. Safety data is summarized as follows:

- The majority of spontaneously reported adverse events were mild to moderate in JBT-101 treated subjects. The most frequent adverse event reported during JBT-101 treatment was mild dry mouth.
- Four of 61 (6.6%) of JBT-101 subjects withdrew following a TEAE, of which two were considered related to JBT-101 including mild lack of cognitive clarity, and a moderate feeling unmotivated. One of 24 (4.2%) of the placebo subjects withdrew following mild difficulty focusing, mild lack of cognitive clarity
- Triplet ECGs with QT/QTc interval measurements were done throughout the trial and showed no significant changes from baseline and similar findings in subjects who received JBT-101 and placebo.
- Overall, changes from baseline in the ARCI-M were similar in subjects who received JBT-101 and placebo.

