3.2.3 Safety Endpoints

Safety will be evaluated by describing incidence of treatment-emergent adverse events (TEAEs) from Visit 1 (Day 1) through 6. TEAEs will be identified by monitoring subject-reported AEs, vital signs, medical history, physical exams, blood and urine safety tests, 12-lead electrocardiograms, and the ARCI-M. Analyses on the following specific events are planned.

- 1. Any Grade 3 or higher AE or SAE that, in the opinion of the blinded site investigator, is at least possibly related to study product. Unless noted otherwise, grading is defined by the National Cancer Institute (NCI) Common Terminology Criteria for Adverse Events (CTCAE) system version 4.0.
- 2. QTc prolongation > 500 msec total duration and > 60 msec from Visit 1 (Day 1) QTc interval prior to study drug administration
- 3. Mild/moderate and severe disease flares by SELENA SLEDAI Flare Index
- 4. BILAG 2004 disease flares, defined as one new BILAG A or two new BILAG B scores
- 5. Aspartate aminotransferase (AST) or alanine aminotransferase (ALT) \ge 3 x upper limit of normal and total bilirubin > 1.5 x the upper limit of normal (confirmed on repeat testing)
- 6. Tolerability, assessed by incidence of discontinuation of study product due to TEAEs at least possibly related to study product from Visits 1 (Day 1) through 5 (Day 85)
- 7. Psychotropic activity, assessed using the ARCI-M

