5.4 Management Plan for Potential Risks

As of July 2017, no severe AEs have been found to be definitely related to JBT-101. As such, the plans detailed in the section are proposed as general precautions for potential risks.

Expected AEs related to JBT-101 are via CB receptors. As of July 2017, a number of the AEs associated with CB1/CB2 agonists have been reported in subjects exposed to JBT-101, such as fatigue, dizziness, decreased concentration, feeling "weird", lightheadedness,

asthenia, somnolence, nausea, vomiting, mild orthostatic hypotension, and dry mouth. Patients in the study will be monitored closely for all of these side effects as well as for potential toxicities including psychotropic, gastrointestinal and cardiovascular effects. They are scheduled to be seen frequently during the treatment period (on study Days 1, 15, 29, 57 and 85) and on day 113 for safety follow-up. The ARCI-M scale will be used to assess psychotropic effects of the drug. The Lupus Activity Patient Global Assessment, PROMIS-29 Short Form and PROMIS Item Bank v2.0 - Cognitive Function will be used to assess fatigue and quality of life. The IVRS e-diary for the NRS scale will be used to record pain on a daily basis. Disease activity will be evaluated using patient history, physical exams, hematologic, blood chemistries, urinalyses and serologies pertinent to the SLEDAI (C3, C4 and anti-dsDNA antibodies).

Prolongations of QTc interval to less than 500 msec total and up to 39 msec prolongation from pre-treatment baseline were observed in a previous Phase 1 study, and all of these prolongations were judged not clinically significant. They were only observed in some subjects ≥ 65 years of age exposed to JBT-101 at a total daily dose of up to 180 mg for seven days. For this reason, to ensure safety of subjects, the QT/QTc interval will be measured throughout the study, and maximum doses tested will not exceed 40 mg/day (given as 20 mg b.i.d.).

If a subject develops a grade 3 or higher NCI-CTCAE (version 4.0) adverse event that is deemed by the blinded site investigator to be possibly related, probably related, or related to study drug, the subject will be discontinued from treatment but will continue to be monitored at the scheduled follow-up visits unless consent is withdrawn.

There will be no dose modification in this study, other than temporary or permanent discontinuation of study drug and there is no rescue treatment.

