7.4 Grading and Attribution of Adverse Events

7.4.1 Grading Criteria

The study site will grade the severity of adverse events experienced by the study subjects according to the criteria set forth in the National Cancer Institute's Common Terminology Criteria for Adverse Events (CTCAE) version 4. This document (referred to herein as the NCI-CTCAE manual) provides a common language to describe levels of severity, to analyze and interpret data, and to articulate the clinical significance of all adverse events. The NCI-CTCAE has been reviewed by the Protocol Chairs and has been deemed appropriate for the subject population to be studied in this protocol.

Adverse events will be graded on a scale from 1 to 5 according to the following standards in the NCI-CTCAE manual:

- Grade 1 = mild adverse event.
- Grade 2 = moderate adverse event.
- Grade 3 = severe and undesirable adverse event.
- Grade 4 = life-threatening or disabling adverse event.
- Grade 5 = death.

For grading an abnormal value or result of a clinical or laboratory evaluation (including, but not limited to, a radiograph, an ultrasound, an electrocardiogram etc.), a treatment-emergent adverse event is defined as an increase in grade from baseline or from the last post-baseline value that doesn't meet grading criteria (i.e. Grade 0, normal). Similarly, changes from screening to baseline will also be recorded as adverse events, but these are not treatment-emergent. If a specific event or result from a given clinical or laboratory evaluation is not included in the NCI-CTCAE manual, then an abnormal result would be considered an adverse event if changes in therapy or monitoring are implemented as a result of the event/result. Grade 2 or higher AEs will be reported on the appropriate AE electronic case report (AE eCRF) for this study.

In addition, for this study, BILAG 2004 disease flares will be graded as follows:

- Mild SLE flare (Grade 1): New BILAG 2004 grade C in one or more organ systems
- Moderate SLE flare (Grade 2): New BILAG 2004 grade B in one or more organ systems
- Severe SLE flare (Grade 3): New BILAG 2004 grade A in one organ system
- Life-threatening or disabling SLE flare (Grade 4): A life-threatening or disabling new BILAG 2004 grade A

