New BILAG flares of Grade 2 or higher (i.e. B or A) will be reported as AEs. Mild/moderate SELENA SLEDAI flares should be reported as AEs if changes in therapy or monitoring are implemented. Severe SELENA SLEDAI flares should be reported as AEs. Signs, symptoms and laboratory test abnormalities reported as part of a SLE flare will not be reported as separate AEs.

7.4.2 **Attribution Definitions**

The relationship, or attribution, of an adverse event to the study therapy regimen or study procedure(s) will initially be determined by the site investigator and recorded on the appropriate AE eCRF. Final determination of attribution for safety reporting will be determined by DAIT/NIAID. The relationship of an adverse event to study therapy regimen or procedures will be determined using the descriptors and definitions provided in Table 4 (below).

Code	Descriptor	Relationship (to primary investigational product and/or other concurrent mandated study therapy or study procedure)				
Unrelated Categories						
1	Not related	The adverse event is clearly not related: there is insufficient evidence to suggest a causal relationship.				
2	Unlikely Related	The adverse event is unlikely related				
Related	Categories					
3	Possibly Related	The adverse event has a reasonable possibility to be related; there is evidence to suggest a causal relationship.				
4	Probably Related	The adverse event is likely related				
5	Related	The adverse event is clearly related.				

Table 4. Attribution of Adverse Events

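### The Grade 2 floor on AE recording has no exception for a mild event that stops study product, so the tolerability endpoint can miss such discontinuations

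*Protocol*

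**What the plan says.** **Recording.** Section 7.3.1 sets the rule: "AEs of Grade 2 and above will be collected from time of signing of informed consent". Section 7.4.1 repeats it: "Grade 2 or higher AEs will be reported on the appropriate AE electronic case report". The same section fixes the meaning of the excluded grade: "Grade 1 = mild adverse event".

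**Attribution.** Under Section 7.4.2 the relationship to study therapy "will initially be determined by the site investigator and recorded on the appropriate AE eCRF".

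**Endpoint.** Item 6 of Section 3.2.3 reads "Tolerability, assessed by incidence of discontinuation of study product due to TEAEs at least possibly related to study product", counted from Visit 1 through Visit 5. It has no grade floor. Nor does the general TEAE incidence in the same section, and Section 8.3.3.1 plans AE summaries by severity grade and relationship.

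**A second recording rule.** Section 7.3.3 tells investigators to record AEs as described in Section 7.2, whose definitions carry no grade limit.

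**Disposition.** Section 8.3.1 summarises early treatment discontinuations with their reasons.

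**Earlier experience (Section 1.3.4).** Four of 61 JBT-101 subjects in the cystic fibrosis trial withdrew following a TEAE. Of these, "two were considered related to JBT-101 including mild lack of cognitive clarity"; the other related case was moderate. The one placebo withdrawal out of 24 followed mild complaints. In the systemic sclerosis trial one of 27 on JBT-101 withdrew for moderate dizziness.

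**The concern.** The endpoint needs three things for each subject who stops: a TEAE, its attribution, and its link to stopping. The first two sit on a form that sites are told to complete only from Grade 2 upward. Section 5.8.1 lets a subject stop at any time on request, and Section 5.4.2 lets the investigator withhold treatment for cannabinoid-type symptoms without a grade threshold. A mild but bothersome effect can therefore end treatment without generating an AE record.

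This is not a detail that an analysis plan could settle later, because an event that was not recorded cannot be recovered at analysis. The trial is meant to describe tolerability and to inform dose selection (Section 1.6), and item 6 is its only endpoint for tolerability. The arms are small, so a single missed case is visible in the reported percentage.

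**Working it through.** **1. Follow one subject through the text.** Suppose a subject stops on Day 20 for a Grade 1 event that the investigator thinks possibly related.

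| Step | Section | Result |
|---|---|---|
| Is the AE collected? | 7.3.1, 7.4.1 | No, below Grade 2 |
| Is it collected under the other rule? | 7.3.3 with 7.2 | Yes, no floor |
| Where is attribution held? | 7.4.2 | AE eCRF, so absent if no AE is entered |
| Does the stop show in disposition? | 8.3.1 | Yes, as a reason |
| Does it count for tolerability? | 3.2.3, item 6 | It should, but not if 7.3.1 is followed |

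Two sites reading different sections would handle the same subject differently. SAEs (7.5.1) and AESIs (7.2.4) are reported whatever their severity, so the gap concerns non-serious mild events outside the AESI list.

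**2. Reproduce the protocol's figures.** Cystic fibrosis, JBT-101: 4/61 = 6.6%, as stated. Placebo: 1/24 = 4.2%, as stated. Systemic sclerosis: 1/27 = 3.7%, as stated.

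**3. Apply the floor to those withdrawals**, reading mild as Grade 1.

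- Related withdrawals on JBT-101, cystic fibrosis: 2/61 = 3.3% at any grade; 1/61 = 1.6% with the floor.
- Placebo, cystic fibrosis: 1/24 = 4.2% at any grade; 0/24 with the floor. Its attribution is not stated, so it would enter an endpoint like item 6 only if judged at least possibly related.
- Adding the systemic sclerosis case, and assuming that it was related (the protocol does not say): (2 + 1)/(61 + 27) = 3/88 = 3.4% at any grade; 2/88 = 2.3% with the floor.

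**4. Carry this to the present trial**, with three active arms of about 25, or 75 subjects.

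- Cystic fibrosis rate: 75 × 2/61 = 2.5 expected, 75 × 1/61 = 1.2 captured, shortfall 1.2.
- Both trials: 75 × 3/88 = 2.6 expected, 75 × 2/88 = 1.7 captured, shortfall 0.9.

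The expected loss is about one subject. In an arm of 25, one subject is 1/25 = 4 percentage points. These rates rest on two or three events and give only an order of size.

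**The case against.** The strongest reply is that the Grade 2 floor is deliberate, applies equally to all blinded arms, and feeds a descriptive safety analysis without formal testing (Section 8.3.3.1). Discontinuations are not invisible, since Section 8.3.1 tabulates reasons. Section 5.4 promises that "Patients in the study will be monitored closely for all of these side effects" and says how: frequent visits, the ARCI-M for psychotropic effects, and the Patient Global Assessment and PROMIS forms for fatigue and quality of life. The ARCI-M has no grade floor, is a safety endpoint in its own right and includes a dry-mouth item. The evidence on withdrawals is also thin: one JBT-101 subject and one placebo subject with mild events, against two JBT-101 subjects with moderate ones.

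Much of this stands. A general Grade 2 rule is a legitimate choice, and the floor does not break the monitoring promise. What it does not answer is item 6: a disposition reason need not carry an AE term, grade or attribution, and no questionnaire links a symptom to stopping.

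A reader might go further and infer that most known drug effects would be lost. The figures that invite this are the pooled list (mild dizziness 21.3%, nausea 12%, dry mouth 8%, somnolence 6% and fatigue 5.3%, against moderate dizziness 10%) and the 55 of 88 extension AEs that were mild (62.5%; the protocol gives 62%). They do not support it:

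- The pooled list covers all doses. Of its 150 subjects, 71 were dosed above the estimated therapeutic range, whereas this trial stops at 40 mg/day. For 60 mg/day or less the protocol gives no split by severity.
- The list shows only entries at 5% or more, so moderate nausea, dry mouth or somnolence below that level may exist and would be collected.
- Of the 88 extension AEs, 75 (85%) were judged unrelated to JBT-101.

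These figures are indicative only and should not be quoted as the share of drug effects lost.

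**Conclusion.** The point holds in a narrow form. Followed as written, Sections 7.3.1 and 7.4.1 leave a discontinuation for a related Grade 1 event out of the tolerability endpoint, although the endpoint's definition includes it. Section 7.3.3 adds a real inconsistency over what sites must record.

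The likely size is about one missed discontinuation among the active arms. This assumes that withdrawal rates resemble those of the earlier trials, that mild there equals Grade 1 here (the earlier grading scale is not given), and that withdrawal there corresponds to stopping study product here. It is a cheap improvement to make, and does not show that the safety data as a whole are inadequate.

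**What to change.** 1. Keep Grade 2 and higher as the general rule. Add to Sections 7.3.1 and 7.4.1 that an AE of any grade is entered on the AE eCRF, with grade and attribution, if it leads to interruption or discontinuation of study product.
2. Align Section 7.3.3 with that rule, so that only one recording threshold is in force.
3. State in Sections 3.2.3 and 8.3.3.1, and in the synopsis, that TEAE incidence otherwise refers to Grade 2 and higher, and that the tolerability endpoint uses events of any grade. Listing the Grade 1 entries with the discontinuations, outside the general incidence table, avoids mixing thresholds.

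Section 7.4.1 already uses an action-based trigger of this kind: mild/moderate SELENA SLEDAI flares are reported, and results not in the grading manual count as AEs, when therapy or monitoring changes. The cost is a few extra eCRF lines, with no added procedure and no change to treatment rules.

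Recording every cannabinoid-type symptom at any grade is a separate choice and not part of this fix. It would add detail on mild dizziness, nausea and somnolence, but would give selected terms a different threshold from the rest of the AE table.

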7.3.2 Collecting Adverse Events

Adverse events (including SAEs) may be discovered through any of these methods:

- Observing the subject.
- Interviewing the subject [e.g., using a checklist, structured questioning, diary, etc.].
- Receiving an unsolicited complaint from the subject.
- In addition, an abnormal value or result from a clinical or laboratory evaluation can also indicate an adverse event, as defined in Section 7.4, *Grading and Attribution of Adverse Events*.

7.3.3 **Recording Adverse Events**

Throughout the study, the investigator will record adverse events and serious adverse events as described previously (Section 7.2, *Definitions*) on the appropriate AE eCRF regardless of the relationship to study therapy regimen or study procedure.

Once recorded, an AE/SAE will be followed until it resolves with or without sequelae, or until the end of study participation, whichever occurs first. End of study participation is the final study visit, either at time of study completion or when a subject prematurely withdraws or is withdrawn.

